#### **1.4. Rationale for Dose Selection**

Sofosbuvir 400 mg, once daily, when dosed in combination with RBV with or without PEG has demonstrated broad genotypic efficacy and favorable safety profile in over 1700 HCV-infected subjects across multiple patient populations in Phase 2 and 3 trials. This dose is the approved marketed dose of sofosbuvir for the treatment of HCV-infection and as such, has been selected for co-formulation with VEL into a fixed-dose combination tablet.

VEL 100 mg has been administered in combination with SOF 400 mg for 12 weeks to 237 HCV-infected subjects in Phase 2 studies. VEL 100 mg was selected for co-formulation with SOF and evaluation in this study based on the Phase 2 safety, PK and antiviral activity (studies GS-US-342-0102, GS-US-342-0109, and GS-US-337-0122 [Cohort 4]). The Phase 1

study GS-US-281-0102 established the anti-HCV activity of VEL and indicated that the exposures achieved following administration of doses > 25 mg provide at least 80% of maximal antiviral response in all HCV genotypes.

The favorable safety and efficacy profiles of SOF 400 mg and VEL 100 mg support further evaluation of this combination and doses in clinical development.

### **1.5. Risk/Benefit Assessment for the Study**

This study will provide information on the safety and efficacy of SOF/VEL, a potent HCV nucleotide inhibitor and a potent HCV NS5A inhibitor. This combination has the potential to be the first once-daily, PEG-free, RBV-free, pangenotypic regimen for the treatment of chronic HCV infection in patients who have received a liver transplant.

The potential benefits of SOF/VEL over the current standard of care for the treatment of chronic HCV are:

- A once-daily, single tablet, single duration, pangenotypic therapy for HCV recurrence in patients with liver transplants could offer PEG-free treatment options to patients with genotypes that currently do not have approved PEG-free regimens
- The once-daily, single tablet, single duration, pangenotypic HCV reoccurrence regimen would offer a simplified algorithm for treatment of HCV recurrence in all patients with liver transplants, regardless of genotype
- A reduction in the AEs currently associated with the use of PEG (particularly for post-transplant patients with genotypes that do not have approved PEG-free regimens) and RBV (for all post-transplant patients, regardless of genotype).
- A reduction in the significant drug-drug interactions that are common amongst patients with liver transplants on complex immunosuppressive regimens.
- A short duration of therapy which should lead to better outcomes through improved adherence.

The safety profile of SOF in clinical studies includes over 1700 chronic HCV-infected subjects that have been administered  $\geq 12$  weeks of SOF and RBV+/-PEG-IFN. No clinical safety issues specifically related to SOF have been identified to date.

The safety profile of SOF + VEL 25mg or VEL 100mg administered for 8 or 12 weeks has been established in over 800 patients in Phase 2 studies. The safety profile of the proposed therapeutic regimen of SOF 400 mg and VEL 100 mg administered for 12 weeks has been established in 237 subjects enrolled in Phase 2 studies. No clinical safety issues specifically related to VEL or SOF + VEL have been identified to date. No clinical safety issues specifically related to the NS5A inhibitor class including daclatasvir (DCV) and LDV have been identified to date {[Afdhal et al 2014a](#), [Afdhal et al 2014b](#), [Kowdley et al 2014](#)}.

The safety profile of SOF/VEL has been studied in 4 Phase 3 trials (ASTRAL 1-4) in 1302 patients. Twelve weeks of SOF/VEL was generally well tolerated, and lead to a similar incidence of AEs and SAEs compared to placebo in patients with GT 1, 2, 4, 5, or 6 HCV (See Section 1.2.2.2.1.1). When 12 weeks of SOF/VEL was compared to SOF + RBV for 12 weeks in patients with GT2 or 3 HCV, therapy with SOF/VEL was again well tolerated with few differences in AEs or SAEs, minus the avoidance of RBV associated toxicities (See Sections 1.2.2.2.2 and 1.2.2.1.3). Patients who received SOF/VEL for either 12 or 24 weeks with decompensated cirrhosis experienced AEs and SAEs typical for patients with decompensated cirrhosis in no pattern that could be attributed to study drug (See Section 1.2.2.1.4). Patients with decompensated cirrhosis who received SOF/VEL + RBV for 12 weeks also experienced AEs and SAEs consistent with underlying liver disease as well as toxicities expected with RBV treatment (See Section 1.2.2.1.4).

In summary, there is no approved Peg-IFN-free or RBV-free treatment available for patients with liver transplants and chronic HCV recurrence. If high rates of SVR can be obtained with a short, IFN-free, RBV-free, pangenotypic regimen, the anticipated improvements in safety and tolerability would offer a favorable risk-benefit ratio for such patients.

#### **1.6. Compliance**

This study will be conducted in compliance with this protocol, Good Clinical Practice (GCP), and all applicable regulatory requirements.

## 2. OBJECTIVES

The primary objectives of this study are:

[figure not shown]
- To evaluate the efficacy of study treatment with sofosbuvir (SOF)/velpatasvir (VEL) FDC for 12 weeks as measured by the proportion of subjects with sustained viral response 12 weeks after cessation of study treatment regimen (SVR12)
- To evaluate the safety and tolerability of the study treatment regimen

The secondary objectives of this study are:

- To determine the proportion of subjects who attain SVR at 4 weeks after cessation of the study treatment regimen (SVR4)
- To evaluate the kinetics of circulating HCV RNA during the study treatment and after cessation of the study treatment regimen
- To evaluate the emergence of viral resistance to SOF and VEL during study treatment and after cessation of study treatment regimen

The exploratory objective of the pharmacogenomics substudy is:

PPD

### **3. STUDY DESIGN**

#### **3.1. Treatment Plan and Regimen**

This is a multicenter, open-label study that will evaluate the safety, tolerability and efficacy of SOF/VEL FDC administered for 12 weeks in subjects with chronic HCV post-liver transplant.

Approximately 80 subjects with recurrent HCV post-liver transplant will be enrolled and treated with SOF/VEL FDC tablet once daily for 12 weeks.

The enrollment target for subjects with GT 3 HCV infection is approximately 20%. The enrollment target for subjects with Metavir stage 3 or 4 fibrosis/cirrhosis or corresponding fibrosis degree is approximately 20%.

The total time to complete all study visits is approximately 28 weeks (30 weeks for those requiring liver biopsy or additional HCV genotype testing at screening):

- 28 day (4 week) screening period (can be extended up to 42 days if liver biopsy, additional HCV genotype testing is required, or for extenuating circumstances)
- 12 week study treatment period
- Up to 12 week post study treatment period

#### **3.2. Visit Schedule**

All subjects will complete screening, on treatment, and post-treatment assessments.

Screening assessments will be completed within 28 days of the Baseline/Day 1 visit. The screening window can be extended to 42 days for subjects requiring liver biopsy, additional HCV genotype testing, or for extenuating circumstances.

All subjects will complete the following study visits: Screening, Baseline/Day 1, on treatment visits at the end of Weeks 2, 4, 8 and 12. All subjects will complete the post-treatment Week 4 visit. Subjects with HCV RNA <LLOQ at the post-treatment Week 4 visit will complete post-treatment Week 12 visit. Subjects with HCV RNA  $\geq$ LLOQ at post-treatment Week 4 or post-treatment Week 12s visit will be asked to return for confirmatory visit.

The assessments performed at each visit are described in Section 6 and [Appendix 2](#).

#### **3.3. HCV Virologic Response-Based Stopping Criteria**

The following on-treatment HCV virologic response-based treatment stopping criteria will be utilized for all subjects:

- Confirmed HCV RNA  $\geq$ LLOQ after 2 consecutive HCV RNA <LLOQ

- Confirmed  $>1 \log_{10}$  increase from nadir
- HCV RNA  $\geq$ LLOQ through 12 weeks of treatment

Confirmation should be performed as soon as possible but within 2 weeks after determination of initial observation indicating virologic failure.

If HCV viral relapse is detected at post-treatment Week 4 or 12 visits, subjects will be asked to return for a confirmatory visit.

### **3.4. Stopping Rules for Individual Subjects**

Subjects who meet any of the following criteria should be discontinued from the study and complete an Early Termination Visit and return for Post-treatment Follow-up visits:

- Elevation of ALT and/or AST that is greater than the ULN and  $> 5x$  baseline or nadir confirmed by immediate repeat testing unless laboratory results are assessed by both the investigator and Gilead Medical Monitor as having an explanation other than drug induced liver injury and it is deemed in the best interest of the subject to continue HCV treatment
- Confirmed elevation of ALT  $>15 x$  ULN (unrelated to any interventional procedures)
- Confirmed total bilirubin  $>10 x$  ULN (unrelated to any interventional procedures)
- Confirmed total bilirubin  $>3x$  baseline or  $3x$  nadir (unrelated to any interventional procedures)
- Any Grade 3 or greater rash associated with constitutional symptoms
- Any non-laboratory Grade 4 events assessed as related to administration of SOF/VEL
- Worsening of disease state as evidenced by progressing hepatic decompensation and/or progression of Child-Pugh Score (CPT) to  $\geq 10$
- Steroid-resistant acute allograft rejection

The Gilead Medical Monitor should be consulted prior to discontinuation of SOF/VEL unless the investigator believes that immediate action is warranted to ensure the continued safety of the subject.

Any questions regarding toxicity management should be directed to Gilead Medical Monitor.

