### **3.6. Assessments for Premature Discontinuation from Study**

If a subject discontinues SOF/VEL dosing (for example, as a result of an adverse event [AE]), every attempt should be made to keep the subject in the study and continue to perform the required study-related post-treatment assessments and procedures (see Section 6.3). If this is not possible or acceptable to the subject or investigator, the subject may be withdrawn from the study.

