### **3.7. Criteria for Discontinuation of Study Treatment**

When medically feasible, the Medical Monitor must be consulted prior to subject discontinuation.

Study drug must be discontinued in the following instances:

- Intercurrent illness that would, in the judgment of the investigator, affect assessments of clinical status to a significant degree
- Unacceptable toxicity, as defined in the toxicity management section of the protocol (Section 7.5), or toxicity that, in the judgment of the investigator, compromises the ability to continue study-specific procedures or is considered to not be in the subject's best interest
- Subject requests to discontinue for any reason; it is important to determine whether the withdrawal of consent is primarily due to an AE, lack of efficacy or other reason
- Subject non-compliance
- Pregnancy
- Discontinuation of the study at the request of Gilead, regulatory agency or an IRB/IEC

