### **7.1.3. Clinical Laboratory Abnormalities and Other Abnormal Assessments as Adverse Events or Serious Adverse Events**

Laboratory abnormalities without clinical significance are not recorded as AEs or SAEs. However, laboratory abnormalities (eg, clinical chemistry, hematology, and urinalysis) that require medical or surgical intervention or lead to IMP interruption, modification, or discontinuation must be recorded as an AE, as well as an SAE, if applicable. In addition, laboratory or other abnormal assessments (eg, electrocardiogram, x-rays, vital signs) that are associated with signs and/or symptoms must be recorded as an AE or SAE if they meet the definition of an AE or SAE as described in Sections 7.1.1 and 7.1.2. If the laboratory abnormality is part of a syndrome, record the syndrome or diagnosis (eg, anemia), not the laboratory result (ie, decreased hemoglobin).

For specific information on handling of clinical laboratory abnormalities in this study, please refer to Section 3.4.

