Infant, <7 Days	6.5 to 7.5 mg/dL 1.61 to 1.88 mmol/L	6.0 to <6.5 mg/dL 1.49 to <1.61 mmol/L	5.5 to <6.0 mg/dL 1.36 to <1.49 mmol/L	<5.5 mg/dL <1.36 mmol/L
Hypercalcemia (corrected for albumin if appropriate*) Adult and Pediatric ≥7 Days	>ULN to 11.5 mg/dL >ULN to 2.88 mmol/L	>11.5 to 12.5 mg/dL >2.88 to 3.13 mmol/L	>12.5 to 13.5 mg/dL >3.13 to 3.38 mmol/L	>13.5 mg/dL >3.38 mmol/L
Infant, <7 Days	11.5 to 12.4 mg/dL 2.86 to 3.10 mmol/L	>12.4 to 12.9 mg/dL >3.10 to 3.23 mmol/L	>12.9 to 13.5 mg/dL >3.23 to 3.38 mmol/L	>13.5 mg/dL >3.38 mmol/L
Hypocalcemia (ionized)	3.0 mg/dL to <LLN 0.74 mmol/L to <LLN	2.5 to <3.0 mg/dL 0.62 to <0.74 mmol/L	2.0 to <2.5 mg/dL 0.49 to <0.62 mmol/L	<2.0 mg/dL <0.49 mmol/L
Hypercalcemia (ionized)	>ULN to 6.0 mg/dL >ULN to 1.50 mmol/L	>6.0 to 6.5 mg/dL >1.50 to 1.63 mmol/L	>6.5 to 7.0 mg/dL >1.63 to 1.75 mmol/L	>7.0 mg/dL >1.75 mmol/L
Hypomagnesemia	1.40 to <LLN mg/dL 1.2 to <LLN mEq/L 0.58 to <LLN mmol/L	1.04 to <1.40 mg/dL 0.9 to <1.2 mEq/L 0.43 to <0.58 mmol/L	0.67 to <1.04 mg/dL 0.6 to <0.9 mEq/L 0.28 to <0.43 mmol/L	<0.67 mg/dL <0.6 mEq/L <0.28 mmol/L

CHEMISTRY				
	Grade 1	Grade 2	Grade 3	Grade 4
Hypophosphatemia Adult and Pediatric > 14 Years	2.0 to < LLN mg/dL 0.63 to < LLN mmol/L	1.5 to < 2.0 mg/dL 0.47 to < 0.63 mmol/L	1.0 to < 1.5 mg/dL 0.31 to < 0.47 mmol/L	< 1.0 mg/dL < 0.31 mmol/L
Pediatric 1 Year–14 Years	3.0 to < LLN mg/dL 0.96 to < LLN mmol/L	2.5 to < 3.0 mg/dL 0.80 to < 0.96 mmol/L	1.5 to < 2.5 mg/dL 0.47 to < 0.80 mmol/L	< 1.5 mg/dL < 0.47 mmol/L
Pediatric < 1 Year	3.5 to < LLN mg/dL 1.12 to < LLN mmol/L	2.5 to < 3.5 mg/dL 0.80 to < 1.12 mmol/L	1.5 to < 2.5 mg/dL 0.47 to < 0.80 mmol/L	< 1.5 mg/dL < 0.47 mmol/L
Hyperbilirubinemia Adult and Pediatric > 14 Days	> 1.0 to 1.5 × ULN	> 1.5 to 2.5 × ULN	> 2.5 to 5.0 × ULN	> 5.0 × ULN
Infant, ≤ 14 Days (non-hemolytic)	NA	20.0 to 25.0 mg/dL 342 to 428 μmol/L	> 25.0 to 30.0 mg/dL > 428 to 513 μmol/L	> 30.0 mg/dL > 513 μmol/L
Infant, ≤ 14 Days (hemolytic)	NA	NA	20.0 to 25.0 mg/dL 342 to 428 μmol/L	> 25.0 mg/dL > 428 μmol/L
Blood Urea Nitrogen	1.25 to 2.50 × ULN	> 2.50 to 5.00 × ULN	> 5.00 to 10.00 × ULN	> 10.00 × ULN
Hyperuricemia	> ULN to 10.0 mg/dL > ULN to 597 μmol/L	> 10.0 to 12.0 mg/dL > 597 to 716 μmol/L	> 12.0 to 15.0 mg/dL > 716 to 895 μmol/L	> 15.0 mg/dL > 895 μmol/L
Hypouricemia Adult and Pediatric 1 year	1.5 mg/dL to < LLN 87 μmol/L to < LLN	1.0 to < 1.5 mg/dL 57 to < 87 μmol/L	0.5 to < 1.0 mg/dL 27 to < 57 μmol/L	< 0.5 mg/dL < 27 μmol/L

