≥ 16 years	3.0 g/dL to < LLN 30 g/L to < LLN	2.0 to < 3.0 g/dL 20 to < 30 g/L	< 2.0 g/dL < 20 g/L	NA

URINALYSIS				
	Grade 1	Grade 2	Grade 3	Grade 4
Hematuria (Dipstick)	1+	2+	3-4+	NA
Hematuria (Quantitative) See Note below				
Females	>ULN - 10 RBC/HPF	> 10-75 RBC/HPF	> 75 RBC/HPF	NA
Males	6-10 RBC/HPF	> 10-75 RBC/HPF	> 75 RBC/HPF	NA
Proteinuria (Dipstick)	1+	2-3+	4+	NA
Proteinuria, 24 Hour Collection				
Adult and Pediatric ≥ 10 Years	200 to 999 mg/24 h	>999 to 1999 mg/24 h	>1999 to 3500 mg/24 h	> 3500 mg/24 h
Pediatric > 3 Mo to < 10 Years	201 to 499 mg/m  /24 h	>499 to 799 mg/m  /24 h	>799 to 1000 mg/m  /24 h	> 1000 mg/ m  /24 h
Glycosuria (Dipstick)	1+	2-3+	4+	NA

Notes:

- Toxicity grades for Quantitative and Dipstick Hematuria will be assigned by Covance Laboratory, however for other laboratories, toxicity grades will only be assigned to Dipstick Hematuria.
- With the exception of lipid tests, any graded laboratory test with a result that is between the LLN and ULN should be assigned Grade 0.
- If the severity of a clinical AE could fall under either one of two grades (e.g., the severity of an AE could be either Grade 2 or Grade 3), select the higher of the two grades for the AE.

CARDIOVASCULAR				
	Grade 1	Grade 2	Grade 3	Grade 4
Cardiac Arrhythmia (general) (By ECG or physical exam)	Asymptomatic AND No intervention indicated	Asymptomatic AND Non-urgent medical intervention indicated	Symptomatic, non-life-threatening AND Non-urgent medical intervention indicated	Life-threatening arrhythmia OR Urgent intervention indicated
Cardiac-ischemia/Infarction	NA	NA	Symptomatic ischemia (stable angina) OR Testing consistent with ischemia	Unstable angina OR Acute myocardial infarction
Hemorrhage (significant acute blood loss)	NA	Symptomatic AND No transfusion indicated	Symptomatic AND Transfusion of ≤ 2 units packed RBCs (for children ≤ 10 cc/kg) indicated	Life-threatening hypotension OR Transfusion of > 2 units packed RBCs indicated (for children ≤ 10 cc/kg) indicated
Hypertension (with repeat testing at same visit)	140–159 mmHg systolic OR 90–99 mmHg diastolic	> 159–179 mmHg systolic OR > 99–109 mmHg diastolic	> 179 mmHg systolic OR > 109 mmHg diastolic	Life-threatening consequences (eg, malignant hypertension) OR Hospitalization (other than ER visit) indicated

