7.2.1. Summaries of Numeric Laboratory Results

Descriptive statistics (n, mean, SD, median, Q1, Q3, minimum, and maximum) will be provided for the “SOF/VEL 12 Weeks” group for ALT, aspartate transaminase (AST), total bilirubin, alkaline phosphatase, hemoglobin, reticulocytes, white blood cells (WBC), neutrophils, lymphocytes, platelets, and international normalized ratio (INR) as follows:

- Baseline values
- Values at each postbaseline visit
- Change from baseline at each postbaseline visit

A baseline laboratory value will be defined as the final assessment performed on or prior to the date of first dose of study drug. Change from baseline to a postbaseline visit will be defined as the visit value minus the baseline value. The mean, median, Q1, Q3, minimum, and maximum will be displayed to reported number of digits, SD to reported number of digits plus 1.

Median (Q1, Q3) of the observed values for ALT, AST, total bilirubin, alkaline phosphatase, hemoglobin, reticulocytes, WBC, neutrophils, lymphocytes, and platelets will be plotted using a line plot for the “SOF/VEL 12 Weeks” group by visit.

In the case of multiple values in an analysis window, data will be selected for analysis as described in Section 3.8.3 (Selection of Data in the Event of Multiple Records in a Window).

The percentage of subjects with at least 1 postbaseline (up to 30 days post last dose) hemoglobin value < 10 g/dL and < 8.5 g/dL will be summarized for the “SOF/VEL 12 Weeks” group. The denominator will be the number of subjects with at least 1 postbaseline hemoglobin value. Note that a subject with a minimum hemoglobin value on treatment of 8.3 g/dL would be counted in both categories.

A listing of subjects meeting the criteria for postbaseline hemoglobin < 10 g/dL and < 8.5 g/dL will be provided.

7.2.2. **Graded Laboratory Values**

The Gilead Grading Scale for Severity of Adverse Events and Laboratory Abnormalities will be used for assigning toxicity grades (0 to 4) to laboratory results for analysis. Grade 0 includes all values that do not meet the criteria for an abnormality of at least Grade 1. Some laboratory tests have criteria for both increased and decreased levels; analyses for each direction (ie, increased, decreased) will be presented separately.

7.2.2.1. **Treatment-Emergent Laboratory Abnormalities**

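### The relative bilirubin stopping rule has no upper-limit-of-normal floor, so a confirmed normal bilirubin can meet a stopping criterion

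*Protocol*

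**What the plan says.** Protocol Section 3.4 lists criteria any one of which means that the subject should be discontinued. Two of the liver criteria are relative to the subject's own baseline or nadir:

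- **ALT/AST.** The bullet opens "Elevation of ALT and/or AST that is greater than the ULN and" and adds a multiple of more than 5 times baseline or nadir. It also carries a waiver: treatment may continue if the investigator and the Medical Monitor agree that there is another explanation and that continuing is in the subject's interest.
- **Total bilirubin.** A confirmed value more than 3 times baseline or 3 times "nadir (unrelated to any interventional procedures"). Confirmation and the procedural exclusion are the only qualifiers. There is no ULN condition and no waiver.

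The bilirubin criterion at more than 10 times ULN is a separate bullet and does not act as a floor for the relative one. Section 7.5.1 only points back to Section 3.4.

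On grading, the Appendix 3 row "Hyperbilirubinemia Adult and Pediatric > 14 Days" starts Grade 1 above 1.0 x ULN. Apart from lipid tests, the Appendix 3 notes say that "any graded laboratory test with a result that is between the LLN and ULN should be assigned Grade 0". SAP Section 7.2.2 agrees: "Grade 0 includes all values that do not meet the criteria for an abnormality of at least Grade 1".

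On handling, Section 3.4 asks for Medical Monitor consultation before SOF/VEL is stopped unless the investigator sees a need for immediate action, and Section 3.7 states: "When medically feasible, the Medical Monitor must be consulted prior to subject discontinuation". Section 3.6 adds that after stopping treatment "every attempt should be made to keep the subject in the study".

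**The concern.** A threefold rise from a low starting value can end inside the normal range. Without a ULN condition, the rule then tells the site to stop a 12-week antiviral course on a value that the study's own grading does not count as a bilirubin abnormality. The ALT/AST rule in the same list avoids this by requiring a value above ULN.

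The instruction is also firmer than Section 3.4 suggests when read alone. Section 3.7 makes stopping mandatory for unacceptable toxicity as defined in Section 7.5, and Section 7.5 consists only of the pointer to Section 3.4.

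At stake is mainly a subject's remaining treatment. There may also be an effect on the primary safety endpoint in Section 8.1.2 (AEs leading to permanent discontinuation of study drug), but that depends on whether such a stop is recorded as an AE. Section 7.1.3 says "Laboratory abnormalities without clinical significance are not recorded as AEs or SAEs" and then requires recording of laboratory abnormalities that lead to discontinuation. It does not say whether a Grade 0 value counts as an abnormality.

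**Working it through.** The plan gives no figure of its own to reproduce here. The check is when the written trigger falls inside the normal range.

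**Inputs**

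- Multiple: 3 times baseline or nadir (Protocol Section 3.4).
- Lower edge of Grade 1: above 1.0 x ULN; in-range values are Grade 0 (Appendix 3).
- Bilirubin ULN: not in the documents. Assumed 1.0 to 1.3 mg/dL.
- Full course: 84 tablets over 12 weeks (SAP Section 4.2.2).
- On-treatment chemistry before the end of treatment: Weeks 2, 4 and 8 (Protocol Sections 6.2.2 and 6.2.3, Appendix 2).

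**Step 1: the condition.** Let r be the baseline or nadir. The trigger is 3r. A normal value can exceed it if and only if 3r < ULN, that is r < ULN/3.

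| r (x ULN) | Trigger, as written | In-range values that meet the rule | Trigger with a ULN floor, max(1, 3r) |
|---|---|---|---|
| 0.20 | > 0.60 | 0.60 to 1.0 | > 1.0 |
| 0.25 | > 0.75 | 0.75 to 1.0 | > 1.0 |
| 0.30 | > 0.90 | 0.90 to 1.0 | > 1.0 |
| 1/3 | > 1.00 | none | > 1.0 |
| 0.40 | > 1.20 | none | > 1.2 |

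The crossover is exactly one third of ULN. At or above it, a floor changes nothing.

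**Step 2: in mg/dL, under the assumed ULN.**

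- Cutoff ULN/3: 1.0/3 = 0.33; 1.1/3 = 0.37; 1.2/3 = 0.40; 1.3/3 = 0.43.
- Reference 0.3: trigger 3 × 0.3 = 0.9, which is 0.9/1.3 = 0.69 to 0.9/1.0 = 0.90 x ULN. In range throughout.
- Reference 0.2: trigger 3 × 0.2 = 0.6, which is 0.6/1.3 = 0.46 to 0.6/1.0 = 0.60 x ULN. In range throughout.
- Reference 0.4: trigger 3 × 0.4 = 1.2, in range only at the top of the assumed span (1.2 < 1.3).

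The nadir can only fall or stay level as visits accumulate, so a subject's trigger cannot rise during treatment. Eligibility sets no lower limit on baseline bilirubin; the bilirubin limit in Section 4.3 is an upper one, on direct bilirubin.

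**Step 3: treatment lost if the stop takes effect at the visit.**

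| Visit | Tablets taken | Share of course | Weeks lost |
|---|---|---|---|
| Week 2 | 14/84 | 16.7% | 12 − 2 = 10 |
| Week 4 | 28/84 | 33.3% | 12 − 4 = 8 |
| Week 8 | 56/84 | 66.7% | 12 − 8 = 4 |

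Confirmation and consultation take time, so the weeks lost are upper limits.

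**Step 4: endpoints.** Stopped subjects return for post-treatment visits (Sections 3.4 to 3.6), so SVR12 can still be observed and a stop is not in itself a failure. If one such stop were recorded as an AE leading to discontinuation, it would add 1/80 = 1.25 percentage points to the primary safety endpoint.

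**The case against.** The strongest reply is that this is a clinical choice. Section 3.4 words each hepatic rule differently, and a more cautious bilirubin trigger is defensible in liver-graft recipients. A within-subject rise and a position against a population limit measure different things, and neither Appendix 3 nor the SAP says that stopping rules must begin at Grade 1. The value must be confirmed, and a confirmed in-range bilirubin is hardly a case for immediate action, so the Medical Monitor would normally be consulted first. No frequency is shown, the weeks lost apply to any stop at those visits, and a protocol change needs approvals at about 18 centers in three countries.

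Much of this stands as a limit on size. The frequency is unknown, the mg/dL figures rest on an assumed ULN, the treatment losses are upper limits, and no effect on a primary endpoint is established. The grading contrast is not a separate defect; it shows what the missing floor leads to.

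It does not remove the problem. The protocol gives no rationale for stopping treatment on a confirmed normal bilirubin. Consultation is not an exception: where an override was intended, in the ALT/AST bullet, it was written in. Continuing treatment after the bilirubin criterion is met would therefore depart from the written rule. Sites also act on rules of this kind: in the ASTRAL-1 safety results (Section 1.2.2.1.1), two placebo subjects stopped for ALT and/or AST at or above 5 times nadir. That is a different analyte and says nothing about how often bilirubin would trigger.

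**Conclusion.** The concern holds. Followed as written, the relative bilirubin rule can be met by a confirmed Grade 0 value whenever baseline or nadir is below one third of ULN. That threshold is exact and needs no assumption. Its translation to 0.33 to 0.43 mg/dL assumes a ULN of 1.0 to 1.3 mg/dL.

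The consequence is limited. An affected subject could lose up to 10, 8 or 4 weeks of treatment, but the number affected cannot be estimated from the documents, confirmation and consultation stand in the way, and SVR12 follow-up is retained. The rule should be corrected, but it does not threaten the primary efficacy analysis.

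**What to change.** In the relative bilirubin bullet of Protocol Section 3.4, add the condition that the confirmed value is also above ULN, so that the criterion becomes total bilirubin > ULN and > 3 times baseline or nadir, with the confirmation requirement and the procedural exclusion kept. Because this narrows a safety rule, the medical lead should agree to it. Leave the bilirubin rule at more than 10 times ULN, the ALT rule at more than 15 times ULN, and the ALT/AST rule with its waiver as they are. Section 3.7 still lets the investigator stop treatment for toxicity or intercurrent illness, so an in-range rise that causes clinical concern can still be acted on.

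The cost is one bullet of wording. No data, visits or procedures are added, since total bilirubin is already part of every chemistry panel. The change needs the approvals described in Section 9.2.1, so it is best carried in the next amendment.
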